7.1.1 Schedule of assessments for probable IPF and Sarcoidosis patients

	Visit 1 Baseline Bronchoscopy	Visit 2 3 months 12-13 weeks post bronchoscopy	Visit 3 6 months 24-26 weeks, post bronchoscopy
	at Bronchoscopy suite at St Mary's Hospital	at Out Patients Clinic at St Mary's Hospital or ICRRU	
Lung function tests (including spirometry and DLco)	X	(X) where clinically indicated	(X) where clinically indicated
Urine	X	X	X
Serum (10 ml) for Biomarkers	X	X	X
Whole blood for RNA 
 • 1st visit (10 ml) • 2nd and 3rd visits miRNA (plasma) and mRNA (gene expression)	X	X	X
Whole blood for DNA (5 ml)	X		

Upper Respiratory Tract sampling	Nasosorption (2 samples)	X	X	X
Bronchoscopy		X		
Lower Respiratory Tract sampling	Bronchosorption (up to 6samples)	X		
	Bronchoalveolar lavage (BAL)	X		

7.2 Visits and study procedures for healthy volunteers

Participants will be required to attend ICRRU on a single day for up to 3 hours. The visit will involve the following;

- **Medical history:**
- Personal details date of birth, next of kin, and gender, ethnicity and contact details will be collected.
- History relating to general health, allergies and drugs (prescription, over the counter and/or herbal medication/ vitamins) will also be collected
- **Smoking History**
A detailed smoking history will be recorded in terms of pack years, start date, current smoking (past 3 months)
- **Physical and nasal examination:**
The study doctor will perform a general physical examination including examination of heart and lungs. In addition, the physician will check the nose to make sure that nasal structure is normal and nasal passages are not blocked.
- **Vital signs:**
Blood pressure, heart rate, respiratory rate and temperature will be checked
Participants' height and weight will be checked

The following samples will be collected in the same way as described in section 7 above

- Blood tests
- Urine Sample
- Nasosorption

Please note there will NOT be any bronchoscopy performed on healthy volunteers.

7.2.1 Incidental findings for healthy volunteers

The study physician will discuss any incidental findings with the participant at point of discovery. With the participant's permission these will be communicated to the participant's General Practitioner where necessary. The study Physician will also institute urgent treatment measures as appropriate.

7.2.2 Schedule of assessments for healthy volunteers

Study procedures	Visit 1 at ICRRU, St Mary's Hospital, Paddington, London
	up to 3 hours
Inclusion and exclusion criteria	review
Blood for serum (10ml)	X
Urine	X
Whole blood for RNA (10ml)	X
Whole blood for DNA (5ml)	X
Nasosorption (left and right nostrils)	X

Sample Management

7.3 Sample Storage and Destruction

Samples collected will be stored up to 10 years, or unless the participants specifically requests that the samples be destroyed, or local laws require destruction of the samples. Samples may also be used in future ethically approved studies where the participants have given written consent. However, if samples have been analysed prior to withdrawal, results from the analysis will remain part of the overall research data.

Data arising from sample analysis, including data on germline mutations, will be subject to confidentiality standards.

7.4 Serum

Fill a 10 ml serum separator tube (SST) completely. It is important to thoroughly mix the blood with the clotting activation agent by inverting the tube not less than five times. Allow blood to clot for 30-60 minutes (tube standing upright). Centrifuge at 1500 x g (\pm 200 x g) for 15 minutes until clot and serum are separated by a well-formed polymer barrier.

Within 20 minutes of the end of centrifugation, use a pipette provided to transfer all serum (upper layer) into an appropriately - labelled 10 ml intermediate tube. Close the cap and invert the tube 10 times to mix the serum.

Use pipette to transfer 1 ml of the serum into each of the four polypropylene tubes labelled "Split 1" through "Split 5".

Freeze all samples immediately at -80°C until the time of shipment on dry ice.

7.5 Whole Blood

7.5.1 Whole blood for DNA

Draw 5 ml blood into 6 ml EDTA tube using standard venepuncture techniques. Mix the blood tube gently by gently inverting tube 5-10 times. Do not shake. Inadequate mixing may result in platelet clumping, clotting and/or incorrect test results. Freeze the sample at -20°C as soon as possible after the draw (must be within 24 hours of draw). Samples should be stored at -80°C until the time of shipment; however, to reduce the risk of tubes cracking, freeze at -20°C first.

7.5.2 Whole blood for RNA

NOTE: You must NOT draw blood directly from the needle into the PAXgene™ Blood RNA tube. You must NOT use a syringe to draw blood and then add it to the tube.

1. After prepping the venepuncture site with an antiseptic and applying a tourniquet, insert the butterfly needle into the patient's vein.
2. It is important that the PAXgene™ Blood RNA tubes are at room temperature (18-25° C) prior to use.
3. Fill all required collection tubes, leaving the 2.5 ml PAXgene™ Blood RNA tubes as the FINAL TUBES to be collected.
4. Hold the PAXgene™ Blood RNA tube vertically, below the patient's arm to avoid air being transferred into the PAXgene™ tube or possible backflow from the tube.
5. Ensure that blood has stopped flowing into the PAXgene™ Blood RNA tube before removing the tube from the holder (at least 10 seconds).
6. Gently invert both PAXgene™ Blood RNA tubes 8-10 times.
7. Store the PAXgene™ Blood RNA tubes upright at room temperature (18-25° C) for 2-3 hours before freezing.
8. Freeze at -20°C until shipment.
9. Place a layer of paper towel between the samples and the dry ice.

WARNING: The contents of the PAXgene™ tube are irritating to the eyes, respiratory system and skin. Refer to the PAXgene™ Blood RNA Product Circular Section IV (Warnings) in the event of an exposure.

7.6 Airway SAM samples

1. Insert each bronchial SAM into a 2 mL micro-centrifuge tube, along with 300µl of Millipore buffer.
2. Vortex mix the sample for 30 s to wash the SAM of loosely attached fluids and biomolecules.
3. To ensure full sample recovery, perform centrifugal elution by adding the moist SAM to a spin filter mini-column that inserts into the same 2 mL micro-centrifuge tube used for washing.
4. Use sterilized forceps to transfer the moist SAM to the spin filter. Change forceps between samples to prevent contamination.
5. Centrifuge samples for 20 min at 16,000 x g in a mini-centrifuge cooled to 4 °C.
6. Aliquot sample eluate as required and freeze at -80 °C

Further details can be found in the manuscript Thwaites et al., 2018 *J. Vis. Exp.* (131) **(35)**.

7.7 BAL samples

BAL samples will be placed immediately on ice following collection. The total volume recovered will be recorded. In the laboratory, BAL samples will be centrifuged at 1200g for 10 minutes. Supernatant will be aliquoted and stored at -80 °C. Cell pellets from BAL will be resuspended in a total of 500µl RNA later and stored at -80 °C.

7.8 Urine Sample

1. Collect a clean catch urine sample into collection cup & store at 4°C (2-4hrs max)
2. Transfer urine into a sterile 50mL screw top plastic centrifuge tube
3. Centrifuge the sample at 1,300xg, 20min, room temperature
4. Decant the supernatant into a new conical tube (being careful not to disturb the pellet in the bottom of the tube)
5. Prepare 5 aliquots of 1mL of the supernatant in low protein binding tubes (GNE usually provides these)
6. Freeze aliquots at -80°C

7.9 Laboratory Procedures, Storage and Shipment

Samples will be barcoded and metadata (including patient number, collection date, sample type, SAM/aliquot #) will be captured by laboratory personnel in internal database/spreadsheets.

Mucosal lining fluid samples will be collected and initially stored frozen at -80 °C without elution. Hence all nasosorption and bronchosorption samples will be stored as non-eluted "samples on SAM" at -80°C in SMH. Prior to shipment to the USA, samples may be eluted and aliquoted according to an agreed elution protocol with a specified buffer at SMH. The weight of nasosorption samples will be recorded.

Serum and urine samples will be aliquoted into 1 ml before storing at -80C to avoid repeated freeze/thaw cycles.

Shipment to Genentech/Roche will be on dry ice. Serum (at least 2ml), Nasosorption (2 SAMs), Bronchosorption (4 SAMs) and BAL will be shipped in two batches; once when all baseline samples have been collected for all patients and once after all time-points (3 months and 6 months) have been collected.

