levels of inflammatory mediators: such as a panel of chemokines and cytokines using the MSD analyser. High detectable levels of mediators of inflammation can then be measured in the bronchial MLF. [name] [name] of the Department of Respiratory Medicine at Saint Mary's Hospital has an extensive experience of successfully sampling over 1000 patients to collect over 1000 bronchosorption samples. The procedure is well tolerated and up to 40µl of fluid is absorbed on a single occasion. The bronchosorption kit is supplied in sterile packs, and has undergone durability and functional testing, and is supplied sterilised by gamma irradiation. In the HRV infection model in patients with allergic asthma and healthy controls, both nasosorption and bronchosorption have been carried out to measure IL-15 (26), IL-25 (27), IL-33 (28) and IL-18 (29). Bronchosorption has been shown to have considerable promise for measuring biomarkers in asthma, and has potential to be used for personalised medicine and selection of specific biologics (30) (31).

[figure not shown]

Figure 1: Bronchosorption device

Bronchoalveolar Lavage (BAL):

As part of the bronchoscopy procedure, the doctor intends to collect a BAL sample. This is done by instilling some sterile fluid into the lung and then drawing this fluid back out again with the bronchoscope. The BAL fluid is then studied to help in the diagnosis of lung diseases. For our study, we will collect this fluid for research purposes.

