3.3 Secondary Outcomes

1. Comparing mediator levels between airway samples (nasosorption and, bronchosorption) within and across the 3 groups (probable IPF, sarcoidosis and healthy controls). Establish significance between groups and correlations across patient groups for sampling types.
2. Comparing mediator levels and mRNA (gene expression) in blood with airway mediator levels across the 3 patient groups, and assessing the degree of correlation.

3. Comparing mediator levels in airway samples and blood with clinical parameters
4. Comparing urine metabolites across the 3 patient groups.

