8.3 Statistical Analysis

Data and all appropriate documentation will be stored for up to 10 years after the completion of the study, including the follow-up period.

The major data will be levels of mediators: periostin, surfactant protein (SPD), CCL18 and CXCL13 in blood and bronchial lining fluid.

We shall perform a test of distribution of data (Shapiro-Wilks test) to check normality of data to ensure appropriate statistical tests are applied to the data.

We shall make individual x-y plots for mediators displaying levels for each individual subject within the patient groups (Probable IPF and sarcoidosis) and healthy controls

Summary Statistics

- Normal data with graphs with means and standard error of means (SEM)
- Non-normal data with graphs with medians, quartiles and ranges (box-whisker)

Paired or unpaired t-tests/ANOVA (or equivalent non-parametric tests) will be used to compare mediator levels in blood and airway mucosal lining fluid within groups over time or between different groups at a single time point.

Correlations will be performed to compare mediator levels in blood, and upper and lower airway mucosal lining fluid samples and clinical parameters in patient groups and healthy controls.

Other graphical and analyses methods like heat maps, violin plots, clustering, multivariate analyses and ROC curves will be used as appropriate.

A *P* value of <0.05 is considered significant.

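### Nasosorption weight is recorded, but Section 8.3 states no use for it in the nasal comparisons and correlations; using it is a cheap improvement for secondary outcomes

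*Combined protocol and SAP*

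**What the plan says.** Section 7.9 of the combined protocol and SAP states: "The weight of nasosorption samples will be recorded". It does not mention a dry or tare weight, when weighing takes place, or what the weight is for. No weight is mentioned for bronchosorption strips.

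Section 7.6 gives one elution volume, for bronchial strips: "Insert each bronchial SAM into a 2 mL micro-centrifuge tube, along with 300µl of Millipore buffer". No nasal buffer volume is given. Section 7.9 adds that, before shipment, "samples may be eluted and aliquoted according to an agreed elution protocol with a specified buffer at SMH". The Introduction says of bronchosorption that "up to 40µl of fluid is absorbed on a single occasion", so uptake varies. It gives no figure for nasal strips.

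In Section 8.3, t-tests or ANOVA, or their non-parametric counterparts, "will be used to compare mediator levels in blood and airway mucosal lining fluid within groups over time or between different groups". It continues: "Correlations will be performed to compare mediator levels in blood, and upper and lower airway mucosal lining fluid samples and clinical parameters". It names no normalisation, dilution factor or covariate. Secondary outcome 1 in Section 3.3 relies on these analyses: "Comparing mediator levels between airway samples (nasosorption and, bronchosorption) within and across the 3 groups". Research question 2 in Section 3.1 asks whether nasal levels track bronchial levels.

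**The concern.** A strip that absorbs more fluid carries more mediator into the same volume of buffer. Two people with the same concentration in their nasal fluid can then give different eluate readings. If that variation is left in, the measured nasal level combines the quantity of interest with a nuisance quantity that the study already plans to measure.

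This matters for two secondary questions. One is whether the less invasive nasal sample can stand in for the bronchial one, where added noise pulls the observed correlation towards zero. The other is the three-group comparison. Healthy volunteers have no bronchoscopy, so every airway comparison with them rests on nasosorption. Section 8.1 also hopes to use this study to size later ones, so spread caused by absorbed volume would carry into those calculations.

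**Working it through.** **No plan figure to reproduce.** Section 8.1 gives no sample size calculation, and the documents give no SD, effect size or power. All SDs and correlations below are assumptions. From the documents come the group sizes (30 probable IPF, 15 sarcoidosis, 15 healthy), the 5% level (taken as two-sided), the 300 µl bronchial buffer volume and the upper figure of 40 µl absorbed.

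**Step 1: mechanism.** With 300 µl of buffer and absorbed volume v, the eluate contains the fraction v/(300 + v) of native fluid:
- v = 10 µl: 10/310 = 3.2%
- v = 20 µl: 20/320 = 6.3%
- v = 40 µl: 40/340 = 11.8%

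The same concentration reads 1.9 times higher at 40 than at 20 µl, and 3.6 times higher at 40 than at 10 µl. The 10 and 20 µl values, and the use of 300 µl for a nasal strip, are assumptions. Any fixed buffer volume acts in the same way.

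**Step 2: attenuation, nasal side only.** On the log scale, measured level ≈ log concentration + log absorbed amount, taken as independent. With SD 0.7 for concentration and s for absorbed amount, the observed correlation is 0.50 × 0.7/√(0.7² + s²). Power uses Fisher's z: Φ(atanh(r)·√(n − 3) − 1.96), ignoring the negligible opposite tail.

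| s | factor | observed r | power, n = 45 | power, n = 30 |
|---|---|---|---|---|
| 0 | 1.00 | 0.50 | 94.5% | 81% |
| 0.3 | 0.92 | 0.46 | 90% | 73% |
| 0.5 | 0.81 | 0.41 | 80% | 61% |
| 0.7 | 0.71 | 0.35 | 67% | 48% |

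For example, at s = 0.7 and n = 45: atanh(0.354) = 0.3695; 0.3695 × √42 = 2.395; Φ(2.395 − 1.96) = 67%. The n = 45 column takes all 30 + 15 patients as having both samples; n = 30 is the IPF group alone.

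**Step 3: noise on both sides.** If bronchial uptake varies equally and independently, the factor is squared. The observed r is then 0.50 × 0.92² = 0.42 at s = 0.3 and 0.50 × 0.71² = 0.25 at s = 0.7. Error-free nasal correction removes one factor and gives 0.46 and 0.35, not 0.50.

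**Step 4: group comparison, 30 v 15.** If mean absorbed amount is equal in the two groups, the false-positive rate stays at 5% and only precision is lost. If it differs by a ratio g with no true mediator difference, the noncentrality is log(g)/[√(0.7² + s²)·√(1/15 + 1/30)] with 43 df. For s from 0.7 to 0.3, the rejection rate is 9-11% at g = 1.2 and 13-19% at g = 1.3.

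**The case against.** The strongest reply is that the documents are silent on adjustment rather than committed to unadjusted levels. A reader might infer that the plan analyses raw eluate readings, but nothing says so. The agreed elution protocol in Section 7.9, or the methods paper cited in Section 7.6, may use the weight before any level reaches the analysis, and neither can be seen here. Section 8.3 also leaves room for multivariate analyses. This stands: the supportable statement is that no use of the weight is given. An analysis rule still belongs in Section 8.3, and if a correction already exists, one sentence there closes the point.

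A reader might also infer that the nasal group comparisons are biased. The documents do not support that. Bias needs absorbed fluid to differ by group, and no evidence of such a difference is given; the rates in Step 4 are conditional on it.

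Three further limits stand. Gross weight is not absorbed fluid, and no dry weight is mentioned, so the covariate is not yet fully in hand. The nasal-bronchial correlation and the nasal group comparison are not the only uses of the nasal samples: Sections 3.3 and 8.3 also plan correlations with blood and clinical measures, and comparisons over time. And if disease itself changes the amount of nasal fluid, conditioning on weight could remove part of a real group difference.

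The exploratory aim lowers the stakes but does not remove the point. Section 8.3 still declares significance at P < 0.05, and choosing a normalisation after seeing the data adds analytic freedom.

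**Conclusion.** The point holds as a cheap improvement to the secondary analyses. The plan records nasosorption weight and states no use for it. With fixed-volume elution, absorbed fluid would add noise to nasal levels and attenuate their correlations.

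Under the assumptions in Step 2, including a noise-free bronchial side, the loss at n = 45 ranges from about 5 to 28 percentage points of power. That sample size assumes that every patient yields both samples and that the two disease groups are pooled. With bronchial noise present, the uncorrected correlation is lower still and nasal correction restores only part of it.

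The primary outcome in Section 3.2 compares bronchial levels between IPF and sarcoidosis and does not depend on nasal weight. A claim that the nasal results are invalid, or that the primary comparison is at risk, would go beyond the documents.

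**What to change.** In Section 7.9, state that each nasosorption strip has a net weight, derived as sample weight minus dry strip weight, and say how the dry weight is obtained. State the nasal elution volume as well.

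In Section 8.3, add wording such as: *Nasal mediator levels will be compared between groups on the log scale with log net nasal sample weight as a covariate. Nasal-bronchial and nasal-blood correlations will also be given as partial correlations controlling for log net nasal weight. Unadjusted results will be reported alongside. Net weight will be compared between groups.*

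The last comparison shows whether bias is possible or only precision is at issue. Showing both sets of results covers the case where disease changes the amount of nasal fluid. If the elution protocol already corrects for absorbed amount, say so in Section 8.3 instead, so that the correction is not applied twice.

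The cost is a few sentences and one derived variable, with no new samples or visits. The one practical requirement is a dry or tare weight, best settled before sampling starts.

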4.3 Sampling

For patients diagnosed with probable IPF and Sarcoidosis, BAL will be collected on the day of their scheduled bronchoscopy. Blood, nasosorption (NS), and bronchosorption (BS) samples will also be collected. Furthermore, on the day of their optional 3 and 6 months follow up visits, we shall collect blood and nasosorption (NS) samples. ***It is important to stress that bronchosorption samples must be taken before BAL or bronchial biopsy samples.*** All patients will have had HRCT of the lung and lung function testing (spirometry and DLco) up to 3 months before bronchoscopy sampling. Healthy volunteers will have a single visit with blood and NS sampling - but no bronchial samples.

With regard to possible coronavirus (COVID-19) infection, this clinical research project will meet Policies and Procedures in conjunction with the NHS, Imperial College London and Public Health England (PHE) guidelines. This will include use of Personal Protective Equipment (PPE) with appropriate clinical facilities and procedures. Appropriate precautions will be taken with sample collection, handling and processing.

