10.1 Sample Shipment

Serum, nasosorption samples, bronchosorption samples, and BAL samples will be shipped to Genentech, San Francisco, California, USA at the end of the study. The samples will be shipped in 2 batches; once when all baseline samples have been collected for all patients and again after all time-points (3 months and 6 months) have been collected.

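### Baseline samples ship in one batch and 3- and 6-month samples in another, with no shared assay run or bridging stated, so tests of change from baseline could pick up a run shift

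*Combined protocol and SAP*

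**What the plan says.** Section 7.9 covers serum, nasosorption, bronchosorption and BAL. It sends them in two batches to the funder's laboratory: "once when all baseline samples have been collected for all patients and once after all time-points (3 months and 6 months) have been collected". Section 10.1 gives the same split ("The samples will be shipped in 2 batches; once when all baseline samples have been collected for all patients") but introduces it by saying that the samples "will be shipped to Genentech, San Francisco, California, USA at the end of the study".

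Serum and nasosorption are the shipped sample types that recur after baseline. Section 4.3 states that "on the day of their optional 3 and 6 months follow up visits, we shall collect blood and nasosorption (NS) samples". Bronchosorption and BAL are taken at Visit 1 only (schedule in 7.1.1), and healthy volunteers have a single visit (4.3, 7.2).

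On elution, 7.9 says that "all nasosorption and bronchosorption samples will be stored as non-eluted", and then that "Prior to shipment to the USA, samples may be eluted and aliquoted according to an agreed elution protocol". Section 7.6 allows eluate to be divided: "Aliquot sample eluate as required and freeze at" −80 °C.

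Section 8.3 plans t-tests or ANOVA, or non-parametric equivalents, on mediator levels in blood and airway lining fluid "within groups over time or between different groups at a single time point", at P<0.05. No section mentions assay timing, a common run or reagent lot, bridging samples, re-assay of baseline material, or a batch term.

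**The concern.** On the plain reading of 7.9 and 10.1, every patient's baseline serum and nasal samples are in shipment 1 and every follow-up sample is in shipment 2. If SAMs are eluted just before each shipment, as 7.9 permits, elution batch follows the same line.

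A shipment is not an assay run. But if each shipment is assayed on arrival, with nothing carried across, run and baseline/follow-up status coincide in every patient. The mean paired difference then estimates true change plus run shift, and the data cannot split the two. A batch term added later would be the same variable as the visit contrast. Healthy volunteers, seen once, give no longitudinal control from which to estimate the shift.

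At stake is the reading of single-group change from baseline in serum and nasal mediators. A significant change could be a laboratory artefact, or a real change could be hidden. The safeguard has to be set before the baseline nasal material is used up.

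**Working it through.** **1. Which contrasts cross the shipment line**

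- IPF versus sarcoidosis in bronchial fluid (primary outcome, 3.2): baseline only, so within shipment 1. Not affected.
- Nasal, bronchial and blood levels at the same visit: within one shipment. Not affected. For comparisons with healthy volunteers this assumes that their samples travel with the patients' baseline samples, which 7.9 does not spell out.
- 3 versus 6 months: both in shipment 2. Not affected.
- Difference in change between IPF and sarcoidosis: crosses the line, but a shift common to both groups cancels.
- Change from baseline within one group, in serum and nasosorption: crosses the line. Affected if the runs are separate and unbridged.

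**2. Size, as illustration only**

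The plan has no figure to reproduce: 8.1 declines a sample size calculation, and no assay variability is given.

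Inputs from the documents: n=30 IPF and n=15 sarcoidosis (4.2), which are maximum numbers of pairs because follow-up is optional; significance level 0.05 (8.3). Assumptions: two-sided paired t-test, no true change, and a constant run shift d in SD units of the paired differences.

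Rejection probability = P(|T| > t(0.975, n−1)), where T is noncentral t with n−1 degrees of freedom and noncentrality d√n. The critical values are 2.045 (n=30) and 2.145 (n=15).

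| d | d√30 | n=30 | d√15 | n=15 |
|---|---|---|---|---|
| 0 | 0 | 5.0% | 0 | 5.0% |
| 0.05 | 0.27 | 5.8% | 0.19 | 5.4% |
| 0.1 | 0.55 | 8.3% | 0.39 | 6.5% |
| 0.2 | 1.10 | 18.5% | 0.77 | 11.2% |
| 0.3 | 1.64 | 35.5% | 1.16 | 19.2% |
| 0.5 | 2.74 | 75.4% | 1.94 | 43.8% |

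The error rate doubles to 10% at d=0.123 (n=30) or d=0.181 (n=15). If two thirds of patients return (assumption; n=20 and n=10), d=0.1, 0.3, 0.5 gives 7.1%, 24.7%, 56.5% and 5.9%, 13.6%, 29.3%.

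In laboratory terms, a 10% multiplicative shift is ln(1.1)=0.0953 on the log scale. With an assumed SD of log change of 0.3, 0.5 or 0.8, d is 0.32, 0.19 or 0.12. The rates are then 39.1%, 17.2%, 9.7% (n=30) and 20.9%, 10.6%, 7.1% (n=15).

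**3. Masking**

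With a true change of 0.5 and an opposing shift of 0.1 or 0.3, the effective d is 0.4 or 0.2. Power falls from 75.4% to 56.3% or 18.5% (n=30), and from 43.8% to 30.3% or 11.2% (n=15).

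**4. Simulation check**

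With 100,000 runs and a within-person correlation of 0.5 (assumed), shifts of 0.1, 0.3, 0.5 in separate runs gave 8.1%, 35.5%, 75.2% (n=30) and 6.5%, 19.0%, 43.6% (n=15). With both visits in one run the rate was 5.0% to 5.1%, as it must be by construction. A two-sample test of change, 30 versus 15 under a common shift, also stayed at 5.0% to 5.1%.

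**The case against.** The strongest reply is that the documents describe shipment and not assay. The receiving laboratory could hold the first shipment and run everything together, and the end-of-study wording in 10.1 is compatible with that. Section 7.9 also refers to an agreed elution protocol, so some laboratory detail is settled elsewhere. This stands as a limit. A reader might infer that the plan assays the visits separately, but the documents do not say so. Nor do they secure a joint run, and the 12-month interim analysis (Sections 2 and 8.2) implies some measurement before follow-up is complete, without saying on which samples.

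Second, change over time is in neither the primary nor the secondary outcomes (3.2, 3.3). It rests on one general sentence in 8.3, in an exploratory study with optional follow-up. That stands, and it lowers the severity.

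Third, the rates show how a t-test responds to any constant bias, not that one is likely here. That stands too: every shift is assumed.

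Fourth, holding all baseline nasal and serum samples until shipment 2 would work against an interim analysis that uses them. It could also separate nasal from bronchial assays, which secondary outcome 1 compares. This is a sound objection to that remedy, and it is why re-assay of reserved aliquots is the main route below.

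**Conclusion.** The point holds in conditional form. The stated shipment rule splits exactly by time point and no safeguard is given. If the shipments are assayed as separate unbridged runs, single-group tests of change from baseline in serum and nasosorption cannot be interpreted, and no later analysis can repair them. Under assumed shifts of 0.1 to 0.5 SD of the paired differences, false positives run from 8.3% to 75.4% at n=30 and from 6.5% to 43.8% at n=15. Below 0.1 SD the problem is slight.

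A reader might go further and conclude that the primary outcome is compromised or that reported changes will be artefacts. The documents support neither: bronchial samples are baseline only, and neither the size nor the existence of a run shift is known. An interim assay could create separate runs within baseline, but that is a different matter from this split. Severity is low to moderate: a cheap improvement worth making before baseline samples are used.

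**What to change.** **Sections 7.9 and 10.1.** State that baseline samples may be assayed early for the interim analysis and for same-visit nasal, bronchial and blood comparisons. For each patient, keep one baseline serum aliquot and one baseline nasal eluate aliquot, and re-assay them in the same run and reagent lot as that patient's 3- and 6-month samples. Reserve the nasal aliquot at elution, at whichever site elutes, with the same elution protocol and buffer at all visits. This must be written down because two nasal samples are collected per visit (7.1.1) and two SAMs are listed for shipment (7.9), so nothing is otherwise left over. Reconcile the end-of-study wording in 10.1 with the two-batch split.

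**Section 8.3.** Use only these same-run values for change from baseline, and record the assay run for every result.

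**Simpler alternative.** If no nasal or serum result is needed before shipment 2, assay all of a patient's visits together once.

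**Cost.** Wording in three sections, with no extra patients, visits or samples. Section 7.4 fills at least four 1 ml serum tubes and 7.9 ships at least 2 ml, so a serum aliquot may already be spare. Baseline serum and nasal aliquots are assayed twice, with one more thaw. Re-assay does not remove differences in elution batch or storage time. The single-run alternative delays nasal and serum results by about 24–26 weeks after the last baseline visit (the Visit 3 window), and would conflict with a 12-month interim analysis that uses those samples.
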